9. PROTECTION OF HUMAN SUBJECTS

9.1 PATIENT DISCONTINUATION

Patients have the right at any time and for any reason to withdraw their consent that their data are collected and used for the study. Reasons for discontinuation of treatment with the ocrelizumab or withdrawal from the study may include, but are not limited to, the following:

- Patient withdrawal of consent at any time
- Patient is lost to follow-up
- · Patient death
- Investigator decision

9.1.1 Discontinuation from Treatment with Ocrelizumab

The decision for discontinuation from treatment lies with the treating physician in agreement with the patient's decision and is not regulated by this protocol. All patients regardless whether continuing or withdrawn from treatment with ocrelizumab will be followed-up by an observation period of at least 7.5 and up to 10 years maximum from study start.

The early termination visit should be completed for patients who discontinue study participation due to e.g. withdrawal of consent or death. The primary reason for treatment discontinuation should be documented on the appropriate eCRF page.

9.1.2 Withdrawal from Study

Every effort should be made to obtain information on patients who withdraw from the study. The primary reason for withdrawal from the study should be documented on the appropriate eCRF page. Patients will not be followed for any reason after consent has been withdrawn. Patients who withdraw from the study will not be replaced.

9.1.3 Lost to Follow-up

For patients whose status is unclear because they fail to appear for study encounters without stating an intention to withdraw, the treating physician will contact the patient in order to assess the patient's interest in continuing study participation. If contact with a missing patient is re-established, follow-up should continue according to the protocol, and exposure and outcome variable information for the missed periods should be collected to the extent possible.

In case of patients changing their treating physician they should continue the study at another participating study site if possible. For patients who change the treating physician to a non-participating site an attempt should be made to diminish the impact of patients being lost from the study when they switch clinical practices. A dedicated neurologist will try to contact the participants directly to collect safety data. This information will be added to the eCRFs. Continued patient consent will be required for this further follow-up.

9.1.4 Study and Site Discontinuation

Roche has the right to terminate this study at any time. Reasons for terminating the study may include, but are not limited to, the following:

- Patient enrollment is unsatisfactory
- Patient safety

Roche will notify the physician if the study is placed on hold, or if Roche decides to discontinue the study.

Roche has the right to replace a site at any time. Reasons for replacing a site may include, but are not limited to, the following:

- Excessively slow recruitment
- Poor protocol adherence
- Inaccurate or incomplete data recording
- Non-compliance with the Guidelines for Good Pharmacoepidemiological Practices (GPP) or any other pertinent local law or guideline

9.2 COMPLIANCE WITH LAWS AND REGULATIONS

This study will be conducted in full conformance with the Guidelines for GPP published by the International Society of Pharmacoepidemiology and the laws and regulations of the country in which the research is conducted.

The study will comply with national and European Union requirements for ensuring the well-being and rights of participants in non-interventional post-authorization safety studies.

9.3 INFORMED CONSENT

Roche's sample Informed Consent Form (and ancillary sample Informed Consent Forms such as a Child's Assent or Caregiver's Informed Consent Form, if applicable) will be provided to each site. If applicable, it will be provided in a certified translation of the local language. Roche must review and approve any proposed deviations from Roche's sample Informed Consent Forms or any alternate Consent Forms proposed by the site (collectively, the "Consent Forms") before EC submission. The final Consent Forms

approved by the EC must be provided to Roche for health authority submission purposes according to local requirements.

The Consent Forms must be signed and dated by the patient or the patient's legally authorized representative before start of documentation of his or her data in the eCRF. The case history or clinical records for each patient shall document the informed consent process and that written informed consent was obtained prior to first documentation of this patient's data in the eCRF.

By signing the form, the patient confirms that he/she has been informed about the study and agrees to pseudonymous data collection, pooling of data with similar scientific data (if applicable), to be contacted in case of contact discontinuation to the study site, and the possibility of monitoring activities. It is the responsibility of the physician to obtain written informed consent from each patient participating in the study, after adequate explanation of the aims, methods, anticipated benefits, and potential hazards of the study. The physician must also explain that the patient is completely free to refuse to enter the study or to withdraw from it at any time, for any reason and without losing the benefit of any medical care to which the patient is entitled or is presently receiving.

A copy of each signed Consent Form must be provided to the patient or the patient's legally authorized representative. All signed and dated Consent Forms must remain in each patient's study file or in the site file and must be available for verification by Site Operations Representative at any time.

9.4 INSTITUTIONAL REVIEW BOARD OR ETHICS COMMITTEE

This protocol, the Informed Consent Forms, any information to be given to the patient, and relevant supporting information must be submitted to the EC by the Site Operations Representative in consultation with the Scientific Responsible and reviewed and approved by the EC before the study is initiated. In addition, any patient recruitment materials must be approved by the EC.

In addition to the requirements for collecting and reporting all AEs, adverse events of special interest (AESI), and SAEs to Roche, physicians must comply with requirements for AE reporting to the local health authority and EC.

9.5 CONFIDENTIALITY

Roche maintains confidentiality standards by coding each patient enrolled in the study through assignment of a unique patient identification number. This means that patient names are not included in datasets that are transmitted to any Roche location.

Patient medical information obtained by this study is confidential and may be disclosed to third parties only as permitted by the Informed Consent Form (or separate authorization for use and disclosure of personal health information) signed by the patient, unless permitted or required by law.

Medical information may be given to a patient's personal physician or other appropriate medical personnel responsible for the patient's welfare, for treatment purposes.

Data generated by this study must be available for inspection upon request by representatives of the U.S. FDA and other national and local health authorities, Roche monitors, representatives, and collaborators, and the EC for each study site, as appropriate.

By signing the protocol, the participating physician commits to complying with all related applicable local laws and regulations, as well as any applicable EU regulations, such as the EU Data Privacy Act.

9.6 FINANCIAL DISCLOSURE

Physicians will provide Roche with sufficient, accurate financial information in accordance with local regulations to allow Roche to submit complete and accurate financial certification or disclosure statements to the appropriate health authorities. Physicians are responsible for providing information on financial interests during the course of the study and for 1 year after completion of the study (i.e., last patient last visit [LPLV]).

10. MANAGEMENT AND REPORTING OF ADVERSE EVENTS/ ADVERSE REACTIONS

10.1 SAFETY REPORTING REQUIREMENTS FOR STUDIED MEDICINAL PRODUCTS

10.1.1 Safety Parameters and Definitions

The reporting requirements in this section apply to all studied medicinal products (observational products of interest, as specifically stated in the study Objectives). For safety reporting requirements for non-studied medicinal products, see Section 10.2.

Safety assessments will consist of monitoring and recording SAEs and non-serious AEs (including AESIs), performing safety laboratory assessments, measuring vital signs, and conducting other tests that are deemed critical to the safety evaluation of the study as per standard medical practice.

10.1.1.1 Adverse Events

According to the International Conference of Harmonization (ICH), an AE is any untoward medical occurrence in a patient or clinical investigation subject administered a pharmaceutical product, regardless of causal attribution. An AE can therefore be any of the following:

 Any unfavorable and unintended sign (including an abnormal laboratory finding), symptom, or disease temporally associated with the use of a medicinal product, whether or not considered related to the medicinal product

- Any new disease or exacerbation of an existing disease (a worsening in the character, frequency, or severity of a known condition), except as described in Appendix 3
- Recurrence of an intermittent medical condition (e.g., headache) not present at baseline
- Any deterioration in a laboratory value or other clinical test (e.g., electrocardiogram [ECG], X-ray) that is associated with symptoms or leads to a change in study treatment or concomitant treatment or discontinuation from study medicine.

10.1.1.2 Assessment of Serious Adverse Events (Immediately Reportable to Roche) and Non-serious Adverse Events of Special Interest (AESI) and Other Non-serious Adverse Events

Serious Adverse Events

An SAE is any AE that meets any of the following criteria:

- · Is fatal (i.e., the AE actually causes or leads to death)
- Is life-threatening (NOTE: The term "life-threatening" refers to an event in which the patient was at immediate risk of death at the time of the event; it does not refer to an event that hypothetically might have caused death if it were more severe.)
- Requires or prolongs inpatient hospitalization (see Appendix 3.3.11)
- Results in persistent or significant disability/incapacity (i.e., the AE results in substantial disruption of the patient's ability to conduct normal life functions)
- Is a congenital anomaly/birth defect in a neonate/infant born to a mother exposed to study medicine
- Is a significant medical event in the physician's judgment (e.g., may jeopardize the patient or may require medical/surgical intervention to prevent one of the outcomes listed above)
- All CTCAE Grade 4 are considered to be an SAE

The terms 'severe' and 'serious' are not synonymous. Severity refers to the intensity of an AE (e.g., rated as mild, moderate, or severe, or according to NCI CTCAE criteria; see Appendix 3); the event itself may be of relatively minor medical significance (such as severe headache without any further findings).

Severity and seriousness need to be independently assessed for each AE recorded on the eCRF (for detailed instructions, see Appendix 3).

Non-Serious Adverse Events of Special Interest

AEs of special interest for this study include the following:

 Cases of potential medicine-induced liver injury that include an elevated ALT or AST in combination with either an elevated bilirubin or clinical jaundice, as defined by Hy's law (see Appendix 3). Suspected transmission of an infectious agent by the study medicine, as defined below:

Any organism, virus, or infectious particle (e.g., prion protein transmitting transmissible spongiform encephalopathy), pathogenic or non-pathogenic, is considered an infectious agent. A transmission of an infectious agent may be suspected from clinical symptoms or laboratory findings that indicate an infection in a patient exposed to a medicinal product. This term only applies when a contamination of the study medicine is suspected.

Exemption of Specific Adverse Events from Collection

AEs which are symptoms of the MS and expected during the course of the disease are not to be recorded in the eCRF.

Medical occurrences or symptoms of deterioration that are anticipated as part of MS or which are expected in the patient population studied should be recorded as an AE only if judged by the physician to have unexpectedly worsened in severity or frequency or changed in nature at any time during the study.

Following the above rationale, all events that are captured in scope of the effectiveness objective, will not be considered as Adverse Events for this study:

- Hospitalizations following an MS relapse as long as the reason for hospitalization is to receive standard treatment with i.v. methylprednisolone, is not considered as SAE
- EDSS progression
- MRI activity (new T2 or Gadolinium enhancing lesion in spinal or cerebral MRI)
- MS signs and symptoms
- Disability
- events originating from patient questionnaires (e.g. fatigue, pain, cognition decline)

As health-related quality of life is a secondary endpoint of this study all AEs reported within the patient-reported outcome using the Treatment Satisfaction Questionnaire for Medication (TSQM1.4), Multiple Sclerosis Impact Scale (MSIS-29 v2), Clinical Global Impression (CGI), and Symbol Digit Modality Test (SDMT) should not be documented per default within the eCRF. During site review of the PRO questionnaire data the physician/study personnel should screen for additional potential safety information out of scope of the questionnaires. If the criteria for an adverse event have been met this must be reported using the Adverse Event eCRF, if not already documented.

As the Pharmacoeconomic outcome 'Work Productivity and Activity Impairment Questionnaire: Multiple Sclerosis (WPAI:MS)' is an exploratory endpoint of this study all AEs reported within the scope of the questionnaire should not be documented per default within the eCRF, but only if not MS-related AEs have been added by the patient.

Deviating laboratory parameters for example: Blood cell count, RBC, hemoglobin, hematocrit, WBC, platelets, immunoglobulins, liver enzymes (ALT, AST, gamma-GT), renal status (creatinine, BUN, unrinalysis), clinical chemistry, flow cytometry, viral serology should only be recorded in the eCRF as an AE when the treating physician considers the deviating laboratory parameters as medical significant.

10.1.2 Methods and Timing for Capturing and Assessing Safety Parameters

The physician is responsible for ensuring that all AEs collected as per protocol (see Section 10.1.1.1 for definition) are recorded in the AE section of the eCRF and reported to Roche in accordance with instructions provided in this section and in Section 10.1.3.

For each AE recorded in the AE section of the eCRF, the physician will make an assessment of seriousness (see Section 10.1.1.2), severity (see Appendix 3), and causality (see Appendix 3).

10.1.2.1 Adverse Event Reporting Period

Physicians will seek information on AEs at each patient contact. All AEs subject to the collecting and reporting requirements outlined in this protocol, whether reported by the patient or noted by study personnel, will be recorded in the patient's medical record and in the AE section of the eCRF.

Once the patient is enrolled in the study, AEs will be collected until the end of his or her observation period. After this period, the physician is not required to actively monitor patients for AEs but if the treating physician becomes aware of any related AEs to any medicinal product they should be notified to the competent authority in the Member State where the reactions occurred or to the marketing authorization holder of the suspected medicinal product, but not to both (to avoid duplicate reporting).

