8.2.2 Study Population

This study will enroll patients with MS from the post-marketing setting who have initiated treatment with ocrelizumab no more than 30 days prior to baseline visit. The decision of the treating physician to prescribe ocrelizumab must have been made for the patients beforehand and independent of participation in this study.

Patients must meet the following criteria for study entry:

- signed informed consent
- have a diagnosis of MS
- aged 18 years or older
- newly treated with ocrelizumab (within 30 days prior to enrollment) according to the local label

Patients who meet any of the following criteria will be excluded from study entry:

 active participation in other interventional and non-interventional studies investigating DMTs for MS

Patients receiving treatment for MS with Ocrelizumab (OCREVUS®) according to standard of care and in line with the current summary of product characteristics (SPC) / local labeling and who have no contraindication to ocrelizumab therapy as per the local label are eligible for observation in this study if written informed consent is provided.

Enrollment of patients will be conducted to ensure 60% of the study population is female in order to adequately power breast cancer event rates in the global PAS studies (BA39730 & BA39731). Sites will be required to maintain a patient screening log of eligible patients reviewed for participation at their treatment centers. This log will document how patients were included or excluded from the study in order to assess the representativeness of the study population.

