 - Action taken with ocrelizumab therapy at the point of diagnosis
 - · AESIs (i.e., Hy's Law and STIAMP only)
 - Death information, if applicable (e.g., date of death, primary and underlying causes of death as entered for the AE)
- Reason for study withdrawal

Scheduled assessments for the study are presented in Table 1 below.

 Table 1
 Data Collection Overview (as per Standard of Care)

ie 1 Data Collection Overview (as p	er Stariuaru bi	Care	
Data Collection ^a	Baseline ^b (Study Enrollment)	Data Collected every ~6 months	Data Collected at Study Completion/ Early Termination Visit
Informed consent ^c	Х		
Inclusion/exclusion criteria	Х		
Patient demographics, height and weight	х		
MS disease history ^d	Х		
MS treatment history ^e	х		
Medical history and comorbidities f	Х		
Malignancy risk factor information ^g	Х		
JCV antibody status / index	Х		
Prior and Concomitant medications h	Х	Х	х
Ocrelizumab administration information i	х	Х	х
Vital signs	Х	Х	х
MS specific symptoms and treatment, relapses ^j		х	х
Clinical management k	Х	Х	х
Laboratory parameters ^I	Х	Х	х
Pregnancy status ^m	Х	Х	х
QoL / PRO ⁿ	Х	Х	х
Pharmacoeconomic outcomes °	Х	Х	х
MRI	Х	Х	х
All serious and non-serious AEs incl. AESIs and information on reasons for death, if applicable	whenever occur		
Pregnancies ^p	whenever occur during treatment with ocrelizumab and within 6 months after last administration		
Any malignancies (incl. NMSCs) and malignancy-specific questionnaire q, s	whenever occur		
Continuation of therapy or Reasons for treatment discontinuation ^{r, s}		х	х
Premature termination incl. reasons for withdrawal ^s		Х	х

AE: adverse event; AESI: adverse event of special interest; MRI: magnetic resonance imaging; MS: multiple sclerosis; NMSC: non-melanoma skin cancer; SAE: serious adverse event; PRO: patient reported outcome; QoL: quality of life; STIAMP: suspected transmission of infection by a medicinal product

- Available data will be collected; no additional diagnostic or monitoring procedures shall be applied to the patients outside of routine clinical practice
- b Up to 30 days prior to first ocrelizumab infusion
- Written informed consent must be obtained before any data collection (per local regulations or ethics committee requirements)
- Including MS date of diagnosis, type of MS, duration of MS, MS disease symptom history, relapse history, EDSS and MRI results (if available)

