8.7.2 Effectiveness Analyses

Effectiveness analyses will be conducted on the Full Analysis Set.

Descriptive analyses of the secondary endpoints will be performed. Secondary variables will be summarized. For continuous data, the mean, standard deviation (SD), median, range (min, max) and interquartile range (Q1, Q3) will be presented. Categorical data will be displayed by absolute and relative frequencies (percentages).

Secondary time-to-event endpoints will be analyzed using Kaplan-Meier product limit methods to estimate the survival distributions and the median time-to-event. The time to endpoint will be defined as an interval between the date of enrolment (date of first visit) and date of first occurrence of the event. For patients who are event free, the censoring time will be calculated as a time interval between date of enrolment and the patient's final contact with available data concerning the event. The estimates and graphical presentation will be performed via Kaplan-Meier approach.

Further analyses will be performed to investigate the validity of results in this non-interventional study, e.g. time-dependent confounding, informative censoring, informative treatment changes/discontinuations, heterogeneity of results, and how to handle missing data. These will be described in the SAP.

Corresponding 95% confidence intervals will be provided, where appropriate.

Full details of the statistical analyses will be described in a SAP.

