8.9 LIMITATIONS OF THE RESEARCH METHOD

This study aims to evaluate the safety profile of ocrelizumab in patients with MS in a real-world setting.

Potential limitations of the study design and measures proposed to address them include the following:

Enrollment bias: Sites will be expected to maintain screening logs of all patients meeting eligibility criteria, along with reasons for non-enrollment.

Channeling bias: Factors associated with treatment choice and also with any of the study outcomes of interest will be measured at baseline (study enrollment), and will be accounted for in multivariate analyses using standard regression-based covariate adjustments or appropriate causal inference methods, as described further in Section 8.7..

Residual confounding between the study population and comparators: Data analysis will examine the univariate distributions of key variables that could cause confounding (e.g., gender, age, comorbidities), and will be accounted for in multivariate analyses.

Healthy user bias/depletion of susceptibles: Long-term users of a given medication may be at lower risk of malignancies than new users (i.e. they would have survived to the time of study enrollment). Since patients will be enrolled at the time of ocrelizumab treatment initiation, this should eliminate bias associated with the study of prevalent medication users.

Misclassification: All centers/sites will undergo standardized training and utilize standardized documentation for completing of eCRFs at enrollment and for each follow-up assessment; specifically, on the importance of accurately collecting exposure information as well as outcome variable information. However, the same rigor may not apply to the data collection in the external control cohorts.

Recruitment of patients dependent on several factors: Uptake of new medications such as ocrelizumab is unpredictable and has the potential to impact the feasibility of meeting the recruitment targets in Germany. However, continuous monitoring of patient recruitment at the site and country levels will allow strategies to be employed in response to any such challenges and to reduce or eliminate the potential impact of these

factors. These include potentially initiation of additional sites within participating countries, and/or expansion of the study into additional countries.

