Appendix 3.3.9 Preexisting Medical Conditions

A preexisting medical condition is one that is present at the screening visit for this study. Such conditions should be recorded on the General Medical History and Baseline Conditions in the eCRF.

A preexisting medical condition should be recorded as an AE only if the frequency, severity, or character of the condition worsens during the study. When recording such events in the AE section of the eCRF, it is important to convey the concept that the preexisting condition has changed by including applicable descriptors (e.g., "more frequent headaches").

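### Patients may enrol up to 30 days after the first infusion, but adverse event collection starts at enrolment and no look-back is required

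*Protocol*

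**What the plan says.** **Entry.** Section 8.2.2 describes patients "who have initiated treatment with ocrelizumab no more than 30 days prior to baseline visit", and the inclusion criterion reads "newly treated with ocrelizumab (within 30 days prior to enrollment) according to the local label". The synopsis, under Milestones, also accepts that exposure can precede the start of data collection by up to 30 days.

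**AE collection.** Section 10.1.2.1, which sets the reporting period, states: "Once the patient is enrolled in the study, AEs will be collected until the end of his or her observation period". The baseline data lists in Sections 8.1 and 8.4.2 contain no AE item.

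**Pre-existing conditions.** Appendix 3.3.9 states: "A preexisting medical condition is one that is present at the screening visit for this study". Such a condition becomes an AE only if it worsens during the study. Table 1 has columns for baseline, six-monthly data and completion or early termination, but none for screening.

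**Denominators.** Under Section 8.7.1 the Safety Set is every enrolled patient with at least one dose, and event rates are per 100 patient-years of treatment exposure.

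**Other anchors.** Table 1 footnote b (Section 8.4.2) defines baseline as "Up to 30 days prior to first ocrelizumab infusion". Section 8.1 equates study inclusion with the start of ocrelizumab. Section 8.7.2 measures time to event as the "interval between the date of enrolment (date of first visit) and date of first occurrence of the event". Section 8.9 says of healthy-user bias: "Since patients will be enrolled at the time of ocrelizumab treatment initiation, this should eliminate bias", and the sentence goes on to limit this to the study of prevalent users.

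**The concern.** The primary outcome is the incidence and type of uncommon AEs, and death, in patients newly exposed to ocrelizumab. For a patient who enrols after the first infusion, exposure has begun but the reporting period has not. The gap can include the first infusion and, for patients enrolled after it, the second initial infusion two weeks later.

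Two rules act on events in that gap. Section 10.1.2.1 does not ask for those already over by enrolment. Appendix 3.3.9, if its screening visit is taken to mean baseline, moves those still present into medical history unless they worsen. The patient still counts in the Safety Set and the exposure time still counts in the rate, so incidence is biased downward for early-onset events.

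The analysis plan cannot repair this, because no analysis recovers events that were never recorded.

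**Working it through.** **1. The plan's own figure.** Section 8.5 asks for 95% probability of seeing at least one AE of 0.1% incidence, under a Poisson model.

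- N = -ln(0.05) / 0.001 = 2996, against about 3000 stated.
- With N = 3000 the expected count is 3000 × 0.001 = 3, and 1 - exp(-3) = 95.0%.

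The figure reproduces, and the Clopper-Pearson limits in Table 2 do so to rounding. The sample size is not in dispute.

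**2. An AE tied to the first infusion.** Let f be the share of patients enrolled after that infusion. The protocol does not give f, so its range is 0 to 100%. Assume that pre-enrolment events are not captured and that risk is the same in early and late enrollees. The expected captured count is 3(1 - f), the detection probability is 1 - exp(-3(1 - f)), and the observed incidence over all 3000 patients is 0.1% × (1 - f).

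| f (assumed) | Expected captured events | Detection probability | Observed incidence |
|---|---|---|---|
| 0% | 3.00 | 95.0% | 0.100% |
| 10% | 2.70 | 93.3% | 0.090% |
| 25% | 2.25 | 89.5% | 0.075% |
| 50% | 1.50 | 77.7% | 0.050% |
| 75% | 0.75 | 52.8% | 0.025% |
| 100% | 0 | 0% | 0% |

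**3. An AE only partly concentrated early.** If a share s of its risk falls before enrolment in late enrollees, detection is 1 - exp(-3(1 - s·f)). At f = 50% this gives 94.2% for s = 10%, 92.8% for s = 25% and 89.5% for s = 50%.

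**4. An AE spread evenly over follow-up.** The most that can be lost is 30 days per patient: 3000 × 30 / 365.25 = 246 patient-years. The minimum planned follow-up is 3000 × 7.5 = 22,500 patient-years, and 246 / 22,500 = 1.1%. This is negligible.

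**5. The baseline window.** Section 8.2.2 puts the first infusion up to 30 days before baseline. Table 1 footnote b puts baseline up to 30 days before the first infusion. Under footnote b no patient would enrol late (f = 0); under Section 8.2.2 f can take any value. A site therefore cannot tell from the protocol whether the gap exists.

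**The case against.** The strongest reply is that Section 10.1.2.1 says when collecting begins but sets no cut-off by onset date. Section 8.4.2 asks for all AEs in the observational period, and Section 8.1 ties inclusion to the start of ocrelizumab. Table 1 has AEs recorded whenever they happen, and Appendix 3.3.1 asks for events within 24 hours of an administration with no exception for the first. A site could read these together and enter first-infusion events retrospectively. That reading is possible, but none of these places sets a start of collection earlier than enrolment. At best, capture would vary across about 250 centers.

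It is also fair that 30 days is trivial against 7.5 to 10 years for most AEs, as step 4 shows, and that f may be small.

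A reader might infer four stronger things that the documents do not support:

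- **Infusion reactions are lost in 17% to 32% of the cohort.** This takes the pivotal-trial incidences of 34.3% and 39.9% and assumes that 50% to 80% of reacting patients react only at the first infusion (0.343 × 0.5 = 17%; 0.399 × 0.8 = 32%). It also needs every patient to enrol after infusion day. At f = 25% it is about 4% to 8%, and these reactions are common, already described events rather than the uncommon AEs on which the study focuses.
- **The enrolment time zero removes primary events.** Section 8.7.2 applies it to secondary time-to-event endpoints only.
- **Section 8.9 claims to have eliminated this bias.** Its statement concerns prevalent-user bias in relation to malignancy. Only its premise, enrolment at treatment initiation, conflicts with Section 8.2.2.
- **Baseline ranges over 30 days either side of the first dose by design.** Two sentences contradict each other; that is not a 60-day window.

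**Conclusion.** The point holds for AEs that arise between the first infusion and enrolment in patients who enrol late. As written, the protocol does not require these events to be collected, can turn persisting ones into medical history, and keeps the patients and their exposure in the primary denominators.

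The size depends on f, which is not stated, and on how far an AE's risk is concentrated early. For a 0.1% AE tied wholly to the first infusion, the planned 95% detection probability falls to 89.5%, 77.7% or 52.8% at f = 25%, 50% or 75%, assuming no retrospective entry. For AEs spread over follow-up the loss is at most about 1.1% of patient-time. The 95% statement in Section 8.5 is therefore sound for most AEs and unsecured only for those of early onset.

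Separately, and without any assumption, Table 1 footnote b contradicts Section 8.2.2.

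**What to change.** 1. In Section 10.1.2.1, state that after consent all AEs with onset since the first infusion are recorded at the enrolment visit and flagged as retrospective. Section 9.3 requires consent only before documentation, so this is feasible.
2. In Appendix 3.3.9, define pre-existing as present before the first infusion, and drop the reference to a screening visit.
3. Reconcile Table 1 footnote b, and the wording in Sections 8.1 and 8.9 that equates enrolment with treatment start, with Section 8.2.2.
4. Keep baseline values taken after the first infusion, but flag them. Accepting only earlier values would discard the baseline questionnaires of late enrollees, since these are not routine and cannot be collected before consent.
5. For the secondary time-to-event endpoints in Section 8.7.2, count time from the first infusion with entry at enrolment (delayed entry). This is a minor change.
6. Qualify, rather than delete, the statement in Section 8.9: patients who died or were lost between first infusion and enrolment cannot enter, and look-back does not recover them. Report them from the screening log that Section 8.2.2 already requires.

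The cost is protocol wording, one extra eCRF flag and some recall error over at most 30 days, at a visit that takes place anyway.
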